Cardiac implantable electronic devices (CIED) are essential therapeutic tools for the management of arrhythmias in different clinical contexts (1, 2). Under the name of CIED are grouped pacemakers and cardiac defibrillators. Worldwide, more than 1 million implants of these devices are carried out annually (3). In Spain CIED implants are made in 230 centers, 4 most CIED are implanted in electrophysiology laboratories by electrophysiologist and the number of implants follows an increasing trend, being in the year 2015 the incidence of pacemaker first implantations/million inhabitants of 611 and that of defibrillators of 118 (5, 6).

A fundamental step in the implant procedure of a CIED is to establish a central venous access in order to insert the electrode catheters and place them in the cardiac chambers. In most procedures ($> 80\%$) it is accessed by the left axilo-subclavian axis, reserving the right side for left-handed patients or with vascular problems on the lefthand side. According to data from the European Heart Rhytm Association (7), 60% of implanters use as a preferential access vein cephalic, 20% axillary vein and 20% subclavian. In our midst, however, this proportion is quite different, with subclavian access being much more widespread.

The access route for the implant of a CIED has prognostic implications. Cephalic access has shown, in the short term, a null incidence of pneumothorax compared with the axillary or subclavian pathway, (8-10) because it does not require puncturing the subclavian region. On the other hand, in the medium and long term, when the access roads are compared, the subclavian approach has been related to a higher incidence of electrode problems as insulation defects and conductor fractures (11-13) which seems due to anatomical factors that condition the electrode's crush (14).

The technique of access through the cephalic vein for the implant of CIED has been carried out for more than five decades (15). Since it requires greater surgical dexterity, it was initially performed preferably by thoracic or cardiac surgeons. With the time, thanks to the technical improvements that have increased their percentage of effectiveness (16-22). However, the main problem for its universalization remains the

lack of knowledge of the technique on the part of many operators and an effectiveness of less than 85%.

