The subclavian vein technique of access for the implant of CIED has been carried out for more than four decades without variations in it (23). It has the advantage of specifying a lower learning curve and being a fast and reliable way of access. The risk of pneumothorax, and the damage problems of the electrodes in the medium and long term, make this technique the least desirable as a way of first choice.

The technique of access through the axillary vein has been the subject of multiple improvements to become a technique that brings together advantages of the previous two (24-28). On the one hand, its speed and low incidence of complications and, on the other, its high effectiveness and capacity to accommodate a greater number of electrodes than the cephalic pathway. However, in our midst it is a technique of scant diffusion among the implanters.

There are some studies that compared the safety and efficacy of venous access techniques in the CIED implant.

Three studies have compared the axillary vein against the subclavian. The retrospective study of Sharma G et al (29), which included 478 patients undergoing a fluoroscopy-guided subclavian or axillary pacemaker implant, showed a similar efficacy of both techniques and a greater incidence of pneumothorax with the subclavian pathway. The retrospective study of Kim KH et al (30), which included 1161 patients with an average follow-up of 8 years, was able to objectively lower long-term incidence of electrode-related complications by the axillary pathway. Finally, the prospective and randomized study of Liu P et al (31) that compared the axillary pathway "optimized" against the subclavian pathway, found a 5 times greater incidence of peri-procedural complications with the second.

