- To compare the success rate of the accesses.
- To compare the duration of access procedures.
- To compare the duration of the implant according to the access.
- To compare the proportion of peri-procedural complications of the accesses.
- To compare the proportion of electrode problems at follow-up.

7) Methodology.

Design: randomized and open clinical trial in parallel groups.

Study population: The reference population is the patients who are implanted for the first time a CIED. The target population of the study will consist of patients who were first implanted with a CIED at the General University Hospital of Ciudad Real.

Selection criteria.

-Inclusion criteria: adults patients (>18 years old) with CIED implant indication at the General University Hospital of Ciudad Real who agree to participate in the study.

-Exclusion criteria: patients with one or more of the following characteristics:

- * pre-existing ipsilateral electrode,
- * ipsilateral lymphadenectomy,
- * cardiac resynchronization therapy indication.

Sample size and sampling procedure.

It is estimated that a sample size of 240 patients is needed for the study to have a 80% statistical power, an alpha value of 0.05 and taking into account the estimated losses due to lack of monitoring and/or data.

The selection of cases that will form the sample shall be conducted by consecutive sampling of all patients who are going to implant a CIED, meet the inclusion and

exclusion criteria, and give their consent to participate in the study. The cases will be allocated to each group (axillary venous access or cephalic venous access) by a procedure of 1:1 randomization by balanced blocks. Sealed envelopes with the number assigned to each of the subjects to be included will contain a card in which the type of venous access assigned will be required.

Period and scope of recruitment.

Patient recruitment will begin in september 2017 and continue until the required sample size is reached with an estimated time limit in december 2019.

Every patient, once recruited and performed the implant of the CIED, will be followed in the same way: before the discharge hospital with review of the device, the surgical wound and the chest X-ray and, later, ambulatory controls at 3, 6, 12 and 24 months of the Device and the generator bag.

The follow-up time will end with the completion of the study, but it may be sooner if the patient dies or moves from the hospital.

Variables:

1. Independent:

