Age, sex, hypertension, diabetes, dyslipidemia, obesity, type of heart disease, renal failure, COPD, CIED indication, type of implanted CIED, assigned access route, number of implanted electrodes, type of electrode implanted.

2. Dependents:

- Efficacy: success of assigned access, duration of the access technique, duration of the procedure, time of copying, cephalic canalization, axillary canalization, finally canalized route, main cause in case of failure.
- Safety: Complications of the procedure, Pneumothorax, hematoma, dislocation electrode, venous thrombosis, long-term electrode problems, insulation defect, driver's fracture, need for new electrode implant.

8) Phases of the project and Plan of work.

The research project will be carried out in the arrhythmia unit of the General University Hospital of Ciudad Real. The two investigators will be in charge of the recruitment of the patients, the implant of the CIED and the data collection. The principal investigator will be in charge of the analysis of the data. Advice and collaboration for analysis will be requested from the HGUCR Research support unit. The commencement of recruitment will be in the fourth quarter of 2017 and completion in the fourth quarter of 2019. No funding is necessary for the realization of the project.

9) Sources of information and data analysis.

The data for the study will be obtained from the patient himself (data of filiation and personal history), of the data collection sheet that will be filled during the implant and in the postoperative and the ambulatory monitoring of the device. All data will be entered in a database with SPSS software for further analysis.

The quantitative variables will be represented by means of the mean +/-standard deviation and the qualitative variables as percentages.

To evaluate the degree of adjustment to the normality of the quantitative variables will be used the test Kolmogorov-Smirnov.

The comparison between the two study groups will be done through an intention-to-treat analysis. The comparison of quantitative and qualitative variables will be carried out with the Student's t test. The comparison of quantitative and qualitative variables with the test of the U of Mann-Withney and the comparison of two Qualitative variables with the χ^2 test. A logistics linear regression analysis will be used for multivariate analysis.

A level of statistical significance shall be considered a value of $p < 0.05$.

10) Ethical aspects.

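### Do the 14 listed independent variables make the multivariate analysis of access route biased or impossible to fit?

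*Combined protocol and SAP*

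**What the plan says.** Section 7, under Variables, lists 14 items as independent. Ten describe the patient or the indication. The other four are "type of implanted CIED, assigned access route, number of implanted electrodes, type of electrode implanted". The randomised factor is therefore on the list, with 13 others.

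Section 9 has a single sentence on modelling: "A logistics linear regression analysis will be used for multivariate analysis". It does not say which outcome is modelled, which variables enter, how they are chosen, or how the result relates to the other analyses. Earlier in the same paragraph, section 9 assigns the comparison of the two arms to an intention-to-treat analysis with Student's t, Mann-Whitney and chi-square tests.

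Section 2 credits the axillary route with "capacity to accommodate a greater number of electrodes than the cephalic pathway" and the cephalic technique with "an effectiveness of less than 85" per cent. On size, section 7 states "It is estimated that a sample size of 240 patients is needed", with "80% statistical power" and "an alpha value of 0.05", under "1:1 randomization by balanced blocks". No complication rate or expected number of events is given.

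**The concern.** There are three grounds for worry.

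- **Post-randomisation covariates.** Electrode number and type are recorded as implanted, after the envelope is opened. If the axillary vein takes more electrodes, the number implanted could be a consequence of the arm. Adjusting for it could then remove or distort part of the effect under test.
- **Too few events.** Access failures and complications look too rare to support 13 covariates plus access route. Estimates could be inflated, or the model might not fit at all.
- **Unclear model.** The sentence in section 9 runs logistic and linear regression together, although the outcomes include both binary events and durations.

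At stake would be a misleading adjusted odds ratio for access route, or a set of covariates chosen after the data were seen.

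**Working it through.** **The plan's own figure.** The total of 240 cannot be tested, because no primary endpoint, rates, sidedness or loss percentage are given. Several assumed inputs reach it. For example, 80% v 93% success, two-sided, needs 108 per arm; with 10% losses, 108/0.90 = 120 per arm, or 240. By contrast, 85% v 95% needs 282 before losses. The event counts below therefore rest on assumed rates.

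**Events per variable if all 14 entered.** With 120 per arm, events = 120 × (cephalic failure + axillary failure), divided by 14.

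| Outcome | Assumption | Events | Per variable |
|---|---|---|---|
| Access failure | cephalic 15%, axillary 1% | 120 × 0.16 = 19.2 | 1.4 |
| Access failure | cephalic 15%, axillary 5% | 120 × 0.20 = 24 | 1.7 |
| Access failure | cephalic 15%, axillary 10% | 120 × 0.25 = 30 | 2.1 |
| Access failure | cephalic 20%, axillary 1 to 10% | 25.2 to 36 | 1.8 to 2.6 |
| Complications | 5% overall | 240 × 0.05 = 12 | 0.9 |
| Single complication | 2% overall | 240 × 0.02 = 4.8 | 0.3 |

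The 15% comes from the background figure in section 2, which may not carry over to the improved technique used here. The other rates are assumptions.

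**What a full model would do.** Trials of 240 patients, 1:1, were simulated with maximum-likelihood logistic regression, 800 runs per setting. The model had 14 single-column terms, or 18 parameters when some factors had several categories. Covariate prevalences and effects were assumed.

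| Mean events | Fit failed, 14 terms | Fit failed, 18 parameters | Mean adjusted log odds ratio (true 1.10) | Mean unadjusted |
|---|---|---|---|---|
| 12 | 27 to 28% | 51 to 55% | 1.27 to 1.54 | 1.13 to 1.18 |
| 18 | 7 to 8% | 24 to 25% | 1.30 to 1.36 | 1.15 to 1.17 |
| 24 | 1 to 3% | 7 to 9% | 1.26 to 1.30 | 1.13 to 1.15 |
| 36 | under 1% | 0.4 to 1.5% | 1.22 to 1.27 | 1.11 to 1.12 |

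At about 5 events, 85 to 97% of fits failed. With a true odds ratio of 1, the mean log odds ratio at 12 to 24 events was -0.02 to 0.06, so there was no clear bias. Coverage of the 95% interval was 93 to 98% at those event counts.

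**Sensitivity to assumptions.** Further simulations used 1,500 trials per scenario, 13 irrelevant covariates and a wider definition of failure (an empty event cell, non-convergence, a standard error above 10, or any coefficient beyond 12 in absolute value). Depending on the assumed prevalences, failure ranged from 0.5 to 19% for 85% v 95% success, 4 to 56% for complications at 5%, and 32 to 83% at 3%. In one such run for success, the true log odds ratio was 1.21, the mean unadjusted estimate 1.28 and the mean adjusted estimate 1.38. Adjustment thus added 1.38 - 1.28 = 0.10.

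**Adjustment for as-implanted variables.** Bias requires the arm to change the number or type of electrodes. Section 2 speaks of what the vein can hold, not of what patients receive. Section 7 excludes resynchronisation. It also records the route finally used and the cause of failure, so another route may serve when the assigned one fails, and the patient may still receive the intended electrodes. Device type probably follows from the indication. The sensitivity simulations used covariates unrelated to outcome, so they cannot show this kind of bias. It is possible but not demonstrated.

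**The case for a change.** The strongest reply is that neither reading of the plan is comfortable. If all 14 variables enter, the model is overloaded. If only some enter, nothing says which. The trial is open, the two investigators recruit, implant and collect the data, and the principal investigator analyses them, so covariates could be picked with results in view. The plan does not expressly label the unadjusted comparison as main or the model as supportive, and one significance level of 0.05 covers both.

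Much of this stands as a description: the model is unspecified, and for rare complications a full model would often not be estimable. But the 14 items are a list of variables to record, set against the dependent ones. Reading them as a model specification is an inference. Section 9 attaches the between-group comparison to the unadjusted tests, so making those the main analysis would restate the plan. Logistic regression for binary outcomes and linear regression for durations is what any analyst would take from the awkward wording. Event counts do not limit the duration models. Which three or four covariates to keep, and whether to bar models for rare outcomes or use a penalised fit, are matters of judgement. Recruitment was planned from 2017 and the document is dated October 2018, so a new field for the planned number of electrodes would need completing in retrospect for patients already enrolled, with no demonstrated gain.

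**Conclusion.** No change is needed. The trial's conclusion on access route rests on the unadjusted intention-to-treat comparison, which neither the variable list nor the multivariate sentence affects. The list has 14 variables, and a model using all of them would have roughly 1 to 2 events per variable for the main binary outcomes under the assumed rates. At 24 events the practical cost is modest: 1 to 9% of fits failed, and a true log odds ratio of 1.10 was estimated at 1.26 to 1.30. At 12 events or fewer it is serious, but an analyst would meet that as a visible fitting failure or implausibly large standard errors and would reduce or drop the model. Bias through the as-implanted variables is plausible for electrode number and type, but unproven.

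This is missing detail about a secondary analysis. The judgement assumes that the report leads with the unadjusted comparison, as section 9 indicates, and treats any adjusted odds ratio as supportive. It would not hold if an adjusted estimate from a long covariate list were presented as the main finding.

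### Two investigators perform the implants, but operator is not a listed variable, the planned comparisons do not adjust for it, and the protocol does not say it is fixed before the arm is known

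*Combined protocol and SAP*

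**What the plan says.** Section 8 (Phases of the project and Plan of work) gives recruitment, implantation and data collection to the same two people: "The two investigators will be in charge of the recruitment of the patients, the implant of the CIED and the data collection". Section 7 (Methodology) describes an open, parallel-group randomized trial.

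The independent variables in section 7 number 14. They are patient and device factors plus the randomized route, and the list ends with "assigned access route, number of implanted electrodes, type of electrode implanted". The efficacy variables begin with "success of assigned access, duration of the access technique, duration of the procedure". Operator appears in neither the independent nor the dependent list.

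Section 9 plans an intention-to-treat comparison of the groups: "The comparison of quantitative and qualitative variables will be carried out with the Student's t test", with the Mann-Whitney test also named and chi-squared for two qualitative variables. A regression is named for multivariate analysis, without an outcome or covariates.

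On allocation, section 7 gives several safeguards. Recruitment is by "consecutive sampling of all patients who are going to implant a CIED". Consent is mentioned ahead of allocation: "give their consent to participate in the study. The cases will be allocated to each group". Concealment is by envelope: "Sealed envelopes with the number assigned to each of the subjects to be included will contain a card". Randomization is 1:1 in balanced blocks. Section 10 adds that the operators are fully trained in both techniques. No section says how or when the operator for a given patient is chosen, and stratification by operator is not mentioned.

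**The concern.** Access success and access time are direct products of the person operating. The protocol's own background points that way: section 2 says the cephalic route demands more surgical skill, and section 4 builds the case for the trial on the lack of comparisons by trained personnel.

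Envelopes, consent and consecutive sampling protect which patient receives which arm. They do not control which of the two investigators does the case once the card has been read. If one operator took more of one arm and was better on average, or better on one route only, part of the operator difference would be reported as a difference between routes. The listed variables could neither reveal this nor correct for it.

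**Working it through.** **Inputs from the documents.** Two implanting investigators (section 8); 240 patients, 1:1, 80% power, alpha 0.05 (section 7); recruitment from September 2017 (section 7) or the fourth quarter of 2017 (section 8) to December 2019; protocol last updated 1 October 2018 (title page). The 240 cannot be reproduced, because no endpoint, effect size, event rate or loss rate is given, so it serves here only as a total.

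**Assumptions.** The documents give no operator gap or split. I take 120 per arm, one operator per implant, no true route effect, a two-sided 5% test, success of 85–90%, an operator gap of 5–10 percentage points for success or 0.25–0.5 SD for time, and an even caseload overall. The 80% power is applied to each outcome in turn, although the protocol ties it to none.

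**Bias.** Operator 1 does a share a of axillary and 1−a of cephalic cases. Let gA and gC be operator 1's advantage on each route. Then bias = (a − 0.5)(gA + gC).
- Same gap g on both routes: (2a − 1)g.
- Gap on one route only: half of that.
- Equal and opposite gaps: zero.

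**Operator independent of arm (a = 0.5).** Bias is 0 in expectation. Adjustment removes a share R² of the variance, and power = Φ(2.802/√(1−R²) − 1.96).
- Time: R² = (d²/4)/(1 + d²/4) = 0.015 (d = 0.25) or 0.059 (d = 0.5); power 80.6% or 82.3%.
- Success: R² = (g/2)²/[p(1−p)] = 0.005 to 0.028; power 80.2% to 81.1%.

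**Moderate sorting (a = 0.6), same gap on both routes.** P(reject) = 1 − Φ(1.96 − b/SE) + Φ(−1.96 − b/SE). For success, SE = √(2p(1−p)/120) = 0.046 (p = 0.85) or 0.039 (p = 0.90). For time, SE = √((2 + (gA² + gC²)a(1−a))/120) = 0.130 (0.25 SD) or 0.133 (0.5 SD).

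| Operator gap | Bias | P(reject) |
|---|---|---|
| 5 points | 1 point | 5.5–5.8% |
| 10 points | 2 points | 7.2–8.1% |
| 0.25 SD | 0.05 SD | 6.7% |
| 0.5 SD | 0.10 SD | 11.7% |

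With a gap on one route only, bias halves (0.5–1 point; 0.025–0.05 SD) and rejection is 5–6% for success and 5–7% for time. With 108 per arm (an assumed 10% loss), the 10-point row becomes 7.0–7.8% and the 0.5 SD row 11.0%.

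**Heavier sorting.** At 80:20 versus 20:80 the bias is (0.6/0.2) = 3 times the 60:40 value; a 10-point gap gives 6 points and rejection of 26–34%. Complete sorting gives five times the 60:40 value.

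**What adjustment can do.** The standard error rises by 1/√(1 − (2a−1)²): 1.02 at 60:40 and 1.25 at 80:20. At complete sorting the factor is infinite, because operator and arm are the same variable. A simulation of the success scenario at 60:40 (40,000 runs per setting, gaps of 5 and 10 points) returned rejection to 5.1–5.4% with stratification by operator. The simulation assigned cases to operators without regard to difficulty.

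**When adjustment can mislead.** Take two equal operators, 85% true success in both arms, and a 60:40 versus 40:60 split. Operator 1's 48 cephalic cases are harder (79%) and operator 2's 72 are easier (89%); axillary cases are taken at random.
- Cephalic overall: 0.4 × 79 + 0.6 × 89 = 85%, so the unadjusted bias is 0.
- Stratified by operator: 0.5 × (85 − 79) + 0.5 × (85 − 89) = 1 point of bias, created by the adjustment.

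**Patients already treated.** With even accrual to 1 October 2018: 13/28 × 240 = 111, or 12/27 × 240 = 107. That leaves 129–133 still to be randomized.

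**The case against.** The strongest reply is that no harm is shown. Nothing in the protocol says or implies that operators are allotted by arm, and section 10 describes both as fully trained in both routes. Its remark about operator preference concerns the choice of route in ordinary practice, which randomization removes here. This stands, and it is why the point is an improvement and not a defect. A reader might infer that the trial's comparison is already confounded by operator; the documents do not support that.

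It is also fair that section 8 does not say each implant has a single operator. If the two work jointly, the sorting model does not apply as written. The variable list is not the case report form either: section 9 refers to "the data collection sheet that will be filled during the implant", whose fields are not reproduced, so operator may already be noted there. The regression names no covariates, so adjustment is unspecified and not excluded. These replies limit what can be claimed. They do not supply a statement that operator is recorded, analysed or fixed in advance.

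A second tempting inference is that putting operator into the model settles the matter for everyone. It does not. Where the operator may have been chosen after the arm was known, operator is a post-randomization variable, and the example above shows that adjusting for it can introduce bias. This part of the objection stands in full and shapes the fix.

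**Conclusion.** The point holds as a low-cost safeguard that should be added. The protocol neither lists operator, nor plans to adjust for it, nor says it is set before the arm is known.

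Its size runs from nothing (operator independent of arm, or equal and opposite operator strengths) to a modest distortion under 60:40 sorting: 1–2 points of success or 0.05–0.10 SD of time, with rejection of 5.5–8% or 7–12% in place of 5%. Heavier sorting is worse, and 80:20 is not a ceiling; complete sorting could not be repaired by any analysis. All these sizes rest on assumed gaps and splits, so they show what the missing information could hide and do not estimate what happened. Confidence is medium, because the documents do not describe how cases are shared between the two investigators.

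**What to change.** 1. Add the operator performing the venous access to the independent variables and to the data collection sheet. For patients already treated, retrieve it where records allow.
2. For every patient still to be randomized, name and record the operator before the envelope is opened. Keep to that operator, or log any change.
3. Tabulate operator by arm, and outcomes by operator and arm.
4. For patients whose operator was fixed before allocation, include that pre-specified operator as a fixed factor in the success analysis (for example, a risk difference stratified by operator, or logistic regression on arm and operator) and in the duration analyses (a linear model, or a stratified Mann-Whitney test if non-normal).
5. For patients treated earlier, report operator adjustment only as a sensitivity analysis, stating that it assumes the choice of operator was unrelated to case difficulty.

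The cost is one field, one model term and two tables. The standard error rises by 2% at a 60:40 split and 25% at 80:20. Operator data may be incomplete for the roughly 107–111 patients treated before 1 October 2018 if accrual was even, since the documents do not describe procedure records. Step 2 can reach only the remaining 129–133.

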Two studies have compared the axillary vein against cephalic. The prospective and randomized study of Calkins H et al (32) compared the safety and efficacy of CIED implant by cephalic access to axillary access guided by venography. It found a higher percentage of success and shorter duration of the procedure by the axillary pathway and there were no differences in the rate of peri-procedural complications. The limitation of this study is that the use of an axillary venous access technique guided by venography limits its applicability and increases the possible complications of the technique. The prospective and randomized study of Squara F et al (33) compared the safety and efficacy of CIED implant by Cephalic access to axillary access guided by fluoroscopy and performed by physicians without any training in the technique. This particular study found no difference in success or complications with both techniques, although it was objective a shorter time to get venous access by axillary. Finally, the prospective observational study of Chan NY et A (113) analyzed the success rate and long-term electrode problems of the techniques of cephalic, subclavian and axillary access guided by venography. The success of cephalic access was significantly lower than the other two. After an average follow-up of 73.6 months, the problem-free survival of the electrode was significantly higher with axillary and cephalic access.

3) Justification.

The studies published so far demonstrate the superiority of the axillary and cephalic venous accesses against subclavian venous access in the CIED implant in terms of efficacy and safety. However, the most widespread venous access technique in our midst remains the subclavian pathway.

There are no recommendations from scientific societies on which access road should be the first choice, so the technique used is totally dependent on the experience and preferences of the implant physician.

To date, there are no studies comparing axillary and cephalic venous accesses performed with the most optimized technique by trained personnel.

4) Hypothesis.

- The axillary venous access pathway is superior in terms of efficacy to the cephalic access.
- The axillary venous access pathway is equal in terms of safety to the cephalic access.

5) Main objective.

To compare the efficacy and safety of fluoroscopy-guided axillary venous access to improved cephalic venous access in the cardiac stimulation device implant.

6) Secondary Objectives:

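### In an open trial the two implanting investigators also collect the outcome data, and nothing stops an operator from scoring their own patients with the route known

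*Combined protocol and SAP*

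**What the plan says.** Section 7 (Design) describes a "randomized and open clinical trial in parallel groups". Section 8 assigns the roles: "The two investigators will be in charge of the recruitment of the patients, the implant of the CIED and the data collection". It adds: "The principal investigator will be in charge of the analysis of the data", with advice to be sought from the hospital's research support unit.

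Section 9 names the patient as the source for identity and history. Outcomes come from a "data collection sheet that will be filled during the implant and in the postoperative and the ambulatory monitoring of the device".

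Section 7 (Variables) gives the efficacy outcomes as "Efficacy: success of assigned access, duration of the access technique, duration of the procedure" and further items, including the vein finally used and the main cause of any failure. The safety list includes pneumothorax, hematoma, electrode dislocation, venous thrombosis and later electrode problems. None has a definition or threshold, and the durations have no start or stop event.

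Follow-up is the same for every patient. It begins "before the discharge hospital with review of the device, the surgical wound and the chest X-ray" and continues with controls at 3, 6, 12 and 24 months.

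Section 4 states the expected result on efficacy: "The axillary venous access pathway is superior in terms of efficacy to the cephalic access". On safety it expects the two routes to be equal.

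**The concern.** The operators cannot be masked, and the open design is not itself a fault. Much of the outcome assessment, however, takes place after the implant, when the assessor could be someone other than the operator. The plan makes no use of this. Whether a swelling is a hematoma, whether a thin line on the film is a pneumothorax, why an access failed, and when access began and ended are all calls that a person must make. Here that person may know the route, may have done the procedure, and has no written definition to apply.

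Both halves of the main objective, efficacy and safety, draw on such items. Intention-to-treat analysis keeps patients in their assigned arm but does not repair an outcome that was recorded wrongly. A larger sample does not shrink the error either.

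**Working it through.** **1. Is there a safeguard anywhere?** Setting the sections side by side:

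| Question | Where | Answer |
|---|---|---|
| Is allocation known? | Section 7, Design | Yes, open |
| Who implants? | Section 8 | The two investigators |
| Who collects data? | Section 8 | The same two |
| Who analyses? | Section 8 | The principal investigator |
| Who reads the wound and X-ray? | Section 7, recruitment and follow-up | Not stated |
| What clock times the access? | Sections 7 and 9 | Not stated |
| Are outcomes defined? | Section 7, Variables | No |
| Masked reader, adjudicator or separate timekeeper? | Whole document | None |

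Self-scoring is therefore permitted, but it is not prescribed.

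**2. Which outcomes are exposed?**
- More exposed: hematoma, borderline pneumothorax, cause of failure, access timing.
- Less exposed: electrode revision, faults measured by the device, and the vein finally used, which limits how far access success can be misreported.

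**3. What could an error do?** The only inputs from the plan are 240 patients, 1:1 allocation and alpha 0.05, so 240 / 2 = 120 per arm before losses. All rates and error sizes below are assumptions. The 240 itself cannot be reproduced, because no endpoint, effect size or loss rate is given, but this point does not depend on it.

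*Hematoma counts, with one third of axillary cases not recorded:*
- True rate 5% in both arms: 120 × 0.05 = 6 v 6. The axillary count becomes 6 − 2 = 4, so 4 v 6.
- True rates 7.5% axillary and 5% cephalic: 120 × 0.075 = 9 v 6. The axillary count becomes 9 − 3 = 6, so 6 v 6.
- Two-sided Fisher p: 9 v 6, 0.60; 6 v 6, 1.0; 4 v 6, 0.75. The estimate moves, but none of these is significant, so the test conclusion stays the same.

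*Any complication, with assumed true rates of 12% axillary and 5% cephalic:* power = Φ((d − 1.96·s0)/s1), where d is the difference in rates, s0 its pooled and s1 its unpooled standard error.
- Full recording: d = 0.070, s0 = 0.0360, s1 = 0.0357, power 49%.
- With 20% of axillary events unrecorded: 0.12 × 0.8 = 0.096, d = 0.046, s0 = 0.0336, s1 = 0.0335, power 28%.

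*Access time, no true difference, a systematic error of b SD in one arm:* the standard error of the difference is √(2/120) = 0.129 SD. The two-sided rejection rate is 1 − Φ(1.96 − b/0.129) + Φ(−1.96 − b/0.129).
- b = 0: 5.0%.
- b = 0.1: b/0.129 = 0.775, giving 12.1%.
- b = 0.2: b/0.129 = 1.549, giving 34.1%.

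Timing is the outcome for which a small systematic error most readily changes a test result.

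**The case against.** The strongest reply is that the documents do not show bias, and that several features limit it. Every patient has the same schedule of device, wound and X-ray review, so differential looking is restrained, although differential classification is not. Several outcomes leave physical or device evidence. The collection sheet is filled in during the implant, so recording is contemporaneous. These points stand, and they narrow the exposed set to the items listed above.

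A reader might infer three stronger things that the text does not support.

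- That each operator does score their own cases. Section 8 assigns data collection to the pair. One may record for the other, although nothing requires it and both may know the route.
- That times are noted by hand or from the operator's memory. The timing source is simply not specified.
- That bias would favour the stated hypotheses. This is a risk, not a fact. For safety the expected result is equality, and the first hematoma example (6 v 6 becoming 4 v 6) moves away from it. Under-recording axillary events pulls towards equality only if axillary access is truly worse.

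It is also fair to say that the hematoma examples mainly show how few events there would be. With perfect scoring, 9 v 6 would still not be significant.

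**Conclusion.** The concern holds as a gap in safeguards. The plan permits unmasked self-scoring by the operators, and judgement-dependent outcomes have neither definitions nor an independent assessor. The documents do not establish that bias will occur, which way it would run or how large it would be. The figures above are illustrations on assumed rates at 120 per arm without losses. They suggest little effect on significance for rare complications at the hematoma rates used, but a material effect on access time if a systematic error reached 0.1 to 0.2 SD. That the principal investigator also analyses the data adds somewhat to the concern. It is worth correcting because the remedy is cheap and misrecorded outcomes are very hard to repair afterwards.

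**What to change.** In section 8, state that the investigator who did not perform the implant scores the pre-discharge wound and chest X-ray and the 3, 6, 12 and 24-month controls. The form should omit the assigned and actual route and be completed before the procedure record is opened.

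In section 7 (Variables), define in advance each outcome that needs judgement, at least hematoma, pneumothorax, access success and the categories for cause of failure. Without definitions a masked scorer has no standard to apply.

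Record access and procedure times in real time from one room clock, using the same start and stop events in both arms. Do not take them from a fluoroscopy log. Axillary access here is guided by fluoroscopy while cephalic access is a surgical technique, so such a log could itself create a timing difference between arms.

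The cost is some scheduling effort and no extra staff. Masking will be imperfect when the scorer attended the implant or when the wound or X-ray reveals the route. The scorer also belongs to the same two-person team. Access success and cause of failure will still be recorded by the operator.
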